4.4.3. Restrictions in 24 Hour Period Prior to PET/CT Exams

- **FDG Scans:** Patients will be asked to minimize physical activity 24 hours prior to scans with FDG. They will also be required to fast for 6 hours prior to the FDG injection. Patients can take all required medications with water.
- **DOTATATE and PSMA Scans:** There are no dietary restrictions for patients prior to receiving PET/CT scans with these tracers.

4.4.4. Day of Study: Single-Tracer FDG PET/CT Exam (all Arms)

FDG PET Tracer Administration:

The patient will be taken to the tracer uptake room, seated comfortably, and have the appropriate IV access placed for tracer administration. The PET technologist will administer approximately 15 mCi of FDG intravenously, and the patient will remain resting during the tracer uptake period (90 min. until start of PET scanning). The patient will be encouraged to hydrate and void their bladder. After the uptake period, the patient will be moved to the PET/CT scanner.

Topogram and CT Scan:

Patients will be positioned on the scanner bed, and will be instructed to remain motionless for the duration of the scan. A CT topogram will be obtained, and the PET imaging field-of-view (FOV) selected. The scanner bed position will be recorded. A CT scan for PET attenuation correction and anatomic localization will then be performed.

Multi-Timepoint PET Scan:

The PET scan will then be acquired, acquiring 5 back-to-back “whole-body” (eyes-to-thighs, or similar) scans, providing 5 sequential PET images. Each pass will take approx. 10 min., for a total scan time of approx. 50 min.

Patient Positioning:

The patient position, bed position, and PET scan FOV will be recorded from the first PET/CT exam. These data will be used to re-position the patient, bed, and FOV for the second PET/CT to match those for the first exam, as possible.

4.4.5. Day of Study: Single-Tracer Cu64-DOTATATE PET/CT Exam (Arm 1)

There are no dietary restrictions for patients prior to the Cu64-DOTATATE PET/CT exam. Patients will be injected with approximately 4 mCi Cu64-DOTATATE, and the tracer uptake time before initiation of PET scanning will be 75 min. All other aspects of the imaging will be identical to that for the FDG PET/CT scan.

4.4.6. Day of Study: Single-Tracer Ga68-DOTATATE PET/CT Exam (Arm 2)

There are no dietary restrictions for patients prior to the Ga68-DOTATATE PET/CT exam. Patients will be injected with approximately 5 mCi Ga68-DOTATATE, and the tracer uptake time before initiation of PET scanning will be 75 min. All other aspects of the imaging will be identical to that for the FDG PET/CT scan.

4.4.7. Day of Study: Single-Tracer PSMA PET/CT Exam (Arm 3)

There are no dietary restrictions for patients prior to the PSMA PET/CT exam. Patients will be injected with approximately 7 mCi Ga68-PSMA-11, and the tracer uptake time before initiation of PET scanning will be 80 min. All other aspects of the imaging will be identical to that for the FDG PET/CT scan.

4.4.8. After Study Procedures

All images will be reconstructed and processed using the same parameters in order to ensure that there are no differences in processing. The PET/CT images will be transferred to the research DICOM database, and de-identified copies will be delivered to MultiFunctional Imaging LLC for processing and analysis according to the Specific Aims of the grant R44CA257522-02.

5.0 METHODS FOR ASSESSMENT OF PET IMAGES

The PET images for each tracer will be evaluated using qualitative visual assessment and semi-quantitative analysis techniques that have previously been used by us and other groups, and represent the standard and accepted means of evaluating static PET images. These assessments will be performed by investigators at HCI, and are described below.

5.1. Qualitative Visual Assessments

Visual assessment of the images for each tracer will be used to qualitatively assess for abnormal focal tracer uptake throughout the imaged body. Images will be reviewed in an unblinded manner to assess whether additional lesions are found when comparing with prior imaging. The coordinates of abnormal foci of uptake will be recorded and semi-quantitative assessments of these lesions will be computed as described below.

5.2. Semi-Quantitative Assessments

Tracer uptake in each lesion identified in the qualitative visual analysis will be quantified by calculating body-weight-corrected Standardized Uptake Values (SUV_{bw}) as follows:

$$SUV_{max} = \frac{A_{max}}{\text{injected activity (mCi)} / \overline{BW}}$$

where $\overline{A_{max}}$ = radioactive concentration (mCi/mL)

\overline{BW} = body weight BW (g)

Corrections for lean body mass will also be performed to calculate the SUV_{lean} as follows:

$$\text{SUV}_{\text{lean}} = (\text{LBM}/\text{BW}) \times \text{SUV}_{\text{bw}}$$

where SUV_{bw} = the SUV measurements using body-weight corrections

LBM = the lean body mass estimated from the Janhasastian Formula [98]

A region-of-interest (ROI) will be drawn over the lesions (on all image slices with abnormal uptake). The mean value in each ROI will be computed to obtain the SUV_{mean} for each tracer, and the maximum value in each ROI will be computed to obtain the SUV_{max} for each tracer.

The location, ROI, SUV_{mean}, and SUV_{max} for each lesion will be recorded and used for data analysis.

6.0 **DATA ANALYSIS AND STATISTICS**

The de-identified images with marked lesion locations will be provided to MFI for further analysis according to the aims of grant 2R44CA257522. The imaging data will be used to develop dual-tracer PET scanning protocols and new processing algorithms for imaging FDG + Cu64-DOTATATE, FDG + Ga68-DOTATE, and FDG + Ga68-PSMA-11. Since a dual-tracer PET image is essentially the sum of two single-tracer PET images, this research will make use of the synthesized dual-tracer evaluation technique summarized below.

6.1. **Synthesized Dual-Tracer Evaluation Technique**

One challenge of evaluating rapid multi-tracer PET techniques is the need to know the ground truth when evaluating results. For example, one possible study design would be to obtain separate, single-tracer scans with each tracer on separate days, and then to obtain simultaneous dual-tracer scans on a 3rd day—all in the same patient. Here the separate-scan images of each tracer could be used as the standard for evaluating images of each tracer recovered from the dual-tracer scans. However, such an approach would pose many problems, in particular: (1) high cost, scheduling challenges, and patient compliance issues for performing 3 different PET/CT exams on 3 different days; (2) increased radiation exposure from 3 PET/CT exams (3 CTs and 4 total PET tracer administrations); (3) test-retest variability for PET is on the order of 10-15% [99-101]—differences that can be larger than the errors in recovered dual-tracer images and thus limit the value of the study; and (4) it would only allow for a single dual-tracer scanning protocol to be studied (rather than allowing for various scanning protocols to be studied and compared).

A better and widely-accepted approach, used by our group and others [2-8, 10-13] is to acquire separate, single-tracer PET scans with each tracer and then retroactively combine the images to “synthesize” dual-tracer images which are ~identical to the images that would have been obtained from actual dual-tracer scanning. When more than one PET tracer is present during a scan, the resulting image represents the sum of all tracer present. As such, the images from separate, single-tracer PET scans can be added together to create “synthesized” multi-tracer PET images. Aside from small differences in scanner deadtime and random coincidence rates (which are well-understood and accurately corrected by the PET scanner), such synthesized dual-tracer images accurately mimic actual multi-tracer PET images, which characteristics that closely match what would have been obtained from actual multi-tracer scanning.

The advantage of this approach is that the actual single-tracer components of the resulting dual-tracer images are known exactly — and they can be used to evaluate the accuracy of individual-tracer images recovered from the multi-tracer images. In effect, the data become their own controls when using this approach.

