2.2.3. FDG, DOTATATE, and Neuroendocrine Tumors

Neuroendocrine tumors, including gastrointestinal NET, pancreatic NET, pulmonary carcinoids, and other rare NET, have an annual incidence of about 5 per 100,000 in the US. Symptoms can be vague, diagnosis is often made at an advanced stage, and selecting the optimal treatment strategy is challenging. Patients with high uptake of DOTATATE (or other SSTR PET tracers) typically have a more indolent tumor and are more amendable to treatment with Lu177 DOTATATE (Lutathera™), while those with high FDG uptake are more aggressive and are best treated by other methods. Combined imaging of FDG and SSTR tracer avidity has previously been proposed for optimal characterization of NETs [34]. Current approaches use biopsies of the initial tumor to assess differentiation status of tumor cells, and then subsequently prescribe either DOTATATE or FDG imaging for well-differentiated and poorly-differentiated tumors, respectively. However, biopsies provide limited sampling, different groups of cells may exhibit different levels of differentiation, and tumors may initially present as well-differentiated but undergo transformation into higher grade over time with the development of treatment resistance [85]. NETs may also exhibit different degrees of differentiation *simultaneously* in the same patient. Combined imaging of FDG+DOTATATE can provide high sensitivity for both well- and poorly-differentiated NETs, improve staging and grading, and provide more accurate prognosis, and predicting effectiveness of targeted radionuclide therapy [26, 32, 86, 87]. Chan *et al.* [35] state “*it is clear that the time has come to think about FDG and SSRI in metastatic NET not as competitors but as complementary imaging modalities*”. Proposed dual-tracer “NETPET scores” [34] and three-scale combined grading system [17] also highlight the need for combined dual-tracer FDG+DOTATATE of NETs.

There are currently 3 DOTA-conjugated peptide PET tracers with FDA approval for localization of somatostatin receptor positive NETs: Cu64-DOTATATE, Ga68-DOTATATE, and Ga68-DOTATOC [16, 20, 26, 27, 38, 48, 49, 88-93]. Each experiences similar uptake and distribution in the body, but have different radioisotopes: Cu64 ($T_{1/2}=12.70$ h, cyclotron-produced, centrally distributed [94, 95]) vs. Ga68 ($T_{1/2}=67.71$ m, generator-produced locally). We include both Cu64 DOTATATE (Arm 1) and Ga68 DOTATATE (Arm 2) in this study.

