2.2.6. Simultaneous Dual-Tracer Imaging Technique

These obstacles can be overcome by simultaneous dual-tracer imaging, where two tracers are administered to the patient and imaged in a single scan. The resultant dual-tracer images would then be processed to recover separate (corrected) images of each tracer. MFI has previously studied patented techniques for rapid *sequential* dual-tracer PET imaging. Under the prior Phase I project, a number of scanning approaches were studied for FDG+DOTATATE and FDG+PSMA imaging, ranging from a simultaneous multi-timepoint scans to sequential back-to-back dynamic scans with each tracer, and evaluated the feasibility and tradeoffs of each. It was found that these tracer pairs could potentially be accurately and robustly recovered from *simultaneous* multi-timepoint imaging as shown in Fig. 1. Here T1-T3 represent multi-timepoint “whole-body” (typically eyes-to-thighs) passes, providing images at 3 timepoints. Proprietary “signal-separation” algorithms at MFI utilize differences in radioactive decay and late tracer kinetics between tracers in order to process the dual-tracer images and recover separate (corrected) images of each tracer. Notably, the imaging characteristics of Cu64 DOTATATE, Ga68 DOTATATE, and PSMA *with respect to* simultaneous imaging with FDG are very similar, and the same signal-separation algorithms and processing can be used. As such, it is efficacious to include all three of these tracer pairs in this study.

If successful, this research will demonstrate the first-ever technique for simultaneous (not sequential) dual-tracer PET imaging of tracer pairs that are being used clinically.

[figure not shown]

Figure 1. Simultaneous FDG+DOTATATE scan protocol (top) and example FDG and DOTATATE images for 30m simultaneous scan (bottom). The recovered FDG and DOTATATE images closely match the true images, with areas of focal uptake (arrows) effectively (but not perfectly) recovered for each tracer.

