6.2.3. Quantitative Performance Targets

The following quantitative performance targets have been set in order to conclude that the new simultaneous dual-tracer techniques provide images of each tracer that are equivalent to images that would be obtained from separate, single-tracer scans of each tracer:

- (1) dual-vs.-single correlation coefficients ≥ 0.95 for both image voxels and lesion SUVs;

- (2) bias, as measured by the linear regression slope, to be within 5% of 1.0 ($0.95 \leq \text{slope} \leq 1.05$);
- (3) bias, as measured by the linear regression intercept, to be within 5% (of mean voxel or SUV value) of zero; and
- (4) tumor and background tissue SUVs for dual-tracer images within 0.05 of those for the separate-scan standard images (to 95% power).

These analyses will be repeated for all 3 tracer pairs.

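### Section 6.2.3 would conclude that simultaneous scanning is equivalent to separate scans, but no simultaneous scan is acquired and only synthesized sums are tested

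*Combined protocol and SAP*

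**What the plan says.** Sections 1.0 and 4.4.2 to 4.4.7 give every subject two single-tracer PET/CT exams on different days. No arm includes a scan with both tracers on board, and no phantom check of the summing step is described.

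Section 6.1 states that "images from separate, single-tracer PET scans can be added together to create" synthesized multi-tracer images. It regards these as nearly identical to acquired dual-tracer images, "Aside from small differences in scanner deadtime and random coincidence rates", and adds that the scanner corrects those differences accurately. It considers a third exam day with a real dual-tracer scan and rejects it for four reasons: cost and compliance, radiation, test-retest variability of 10-15%, and being tied to a single scanning protocol.

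Section 6.2 compares each recovered image with a reference called true, defined as the single-tracer image that went into the sum. Section 6.2.3 sets four targets: correlation of at least 0.95, slope from 0.95 to 1.05, intercept within 5%, and SUVs within 0.05. Meeting them is to support the conclusion that the simultaneous techniques give images "equivalent to images that would be obtained from separate, single-tracer scans of each tracer".

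**The concern.** The conclusion is about a scanning technique; the evidence is about an algorithm applied to arithmetic sums. The two coincide only if a sum behaves like a joint scan in every respect that matters to the targets, and the plan asserts this without testing it.

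Two features separate them. First, the reference is an addend of the tested image, so its noise is present in both. A recovered image from a real joint scan would carry noise independent of a separately acquired reference. Agreement, including the voxel correlation target, is therefore not measured under the conditions of a real comparison. Second, random coincidences grow with the square of the singles rate, so a joint scan contains a cross-term between the tracers that two separate scans do not. Section 6.1 calls the difference small but gives no figure.

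At stake is the headline claim. If the targets are met, readers would be told that simultaneous scanning can stand in for two separate scans, when no simultaneous scan was made.

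**Working it through.** **Plan's own figures.** The documents give no figure for randoms, so there is none to reproduce. The one statistical figure, N = 104 in Section 6.3, does reproduce: 2 × [(1.960 + 1.645) × 10/5]² ≈ 104, the normal-approximation size per group for two independent means. This point does not depend on it.

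**Inputs from the protocol.**
- FDG, Section 4.4.4: "administer approximately 15 mCi of FDG intravenously", scan start at 90 min, five passes "for a total scan time of approx. 50 min".
- Second tracer, Sections 4.4.5 to 4.4.7: Cu64-DOTATATE 4 mCi at 75 min; Ga68-DOTATATE 5 mCi at 75 min; Ga68-PSMA-11 7 mCi at 80 min.
- Half-lives, Section 2.2.3: Cu64 12.70 h (762 min); Ga68 67.71 min.

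**Assumptions not in the documents.**
- F18 half-life 110 min (90 to 130 tried).
- Positron yields F18 0.967, Ga68 0.889, Cu64 0.174.
- Singles proportional to activity × yield, and randoms to singles squared.
- Physical decay only, and a joint scan at these same activities and uptake times.

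**Step 1: activity in mCi, A × 2^(−t/T).**

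| Tracer | Scan start | 50 min later |
|---|---|---|
| FDG | 15 × 2^(−90/110) = 8.51 | 6.21 |
| Cu64-DOTATATE | 4 × 2^(−75/762) = 3.74 | 3.57 |
| Ga68-DOTATATE | 5 × 2^(−75/67.71) = 2.32 | 1.39 |
| Ga68-PSMA-11 | 7 × 2^(−80/67.71) = 3.09 | 1.85 |

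**Step 2: singles of the second tracer relative to FDG at scan start, r.**
- Arm 1: (3.74 × 0.174)/(8.51 × 0.967) = 0.08
- Arm 2: (2.32 × 0.889)/(8.51 × 0.967) = 0.25
- Arm 3: (3.09 × 0.889)/(8.51 × 0.967) = 0.33

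**Step 3: randoms in a joint scan relative to the two scans summed.** The ratio is (a + b)²/(a² + b²) = (1 + r)²/(1 + r²). It cannot exceed 2, which it reaches at r = 1.

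| Arm | Scan start | 50 min later | Scan start, no yield weighting |
|---|---|---|---|
| 1 | 1.16 | 1.20 | 1.74 |
| 2 | 1.47 | 1.40 | 1.51 |
| 3 | 1.60 | 1.51 | 1.64 |

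**Step 4: sensitivity.** Varying the F18 half-life from 90 to 130 min without yield weighting gives 1.47 to 1.56 in Arm 2 and 1.60 to 1.70 in Arm 3 at scan start. Those two arms depend little on the assumed constants. Arm 1 depends heavily on the assumed Cu64 yield, and counting singles by positron yield alone understates Cu64's other emissions, so its figure is the least secure.

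**Step 5: from randoms to the targets.** Subtracting estimated randoms corrects the expected counts but leaves their variance. The synthesized sum lacks the variance of the cross-term. Turning that into a change in correlation, slope, intercept or SUV needs count rates or randoms fractions, which the documents do not give. The calculation stops here.

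**The case against.** The design is disclosed and argued. Section 6.1 weighs a real dual-tracer scan and gives sensible reasons against it, and the primary objective in Section 1.1 is to obtain data for development. That stands as a defence of the design. It does not widen what the design can show.

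Section 6.1 also says the scanner corrects deadtime and randoms. That stands for the mean: a ratio of 1.5 in randoms is not a bias of that size in any image. A reader might infer that the targets would be met or missed wrongly; the documents do not support this, because no effect on them can be computed.

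The ratios rest on outside constants and on a joint scan at the single-tracer activities and timings. Section 2.2.6 illustrates a three-timepoint scan, and Section 6.1 wants several protocols compared. The figures therefore test the word small; they do not predict a particular scan.

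Three stronger readings are tempting.
- **Cu64 over-weighted about five-fold in Arm 1.** With the assumed yields, adding images already corrected for positron yield would over-weight Cu64 by 0.967/0.174 = 5.6 (5.1 to 5.9 over the yields tried) and Ga68 by 1.07 to 1.14. No section prescribes such a sum. Section 6.2 says only that the images are combined, and it bases the algorithms on differences in decay, which adding decay-corrected images would erase. The concentration unit in Section 5.2 defines the SUV, not the summation. The step is unspecified, not shown to be wrong.
- **Arm 1 results would be flattered.** The same hypothetical sum would remove the decay contrast, which makes separation harder, and more Cu64 signal would contaminate FDG. No direction is established.
- **Section 2.2.6 contradicts the half-lives.** Its remark that the tracers' imaging characteristics "are very similar, and the same signal-separation algorithms and processing can be used" is background, limited to imaging with FDG, and follows a sentence naming decay differences as a basis for separation. Section 2.2.3 says openly of the somatostatin-receptor tracers: "Each experiences similar uptake and distribution in the body, but have different radioisotopes".

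**Conclusion.** The concern holds for the conclusion in Section 6.2.3. It follows from the documents alone that no simultaneous scan is acquired and that the reference is a component of the tested image. Meeting the four targets would support accurate recovery from synthesized sums and nothing wider.

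The supporting point, that the differences in Section 6.1 are not evidently small, rests on the stated assumptions about F18 half-life, positron yields and joint-scan timing. On those, randoms rise by about 40-50% in Arm 2, 50-60% in Arm 3 and 15-20% in Arm 1, with Arm 1 the least certain. The consequence is extra noise of unknown size, not a demonstrated bias.

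**What to change.** **Section 6.2.3.** Restate what the targets establish, for example: *meeting these targets supports the statement that the algorithms recover each tracer's image accurately from synthesized dual-tracer images; performance on acquired simultaneous scans is not evaluated here.* Do not claim equivalence of the simultaneous technique itself on these data.

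**Section 6.1.** Drop or qualify the near-identity statement and the word small. Say that randoms correction addresses the mean, that the added noise of a joint scan is absent from the sum, and that the tested and reference images share noise.

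**Secondary clarification, Section 6.1.** State that each image is returned to its as-measured decay and positron-yield scale before summation. This matters most for Cu64.

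The cost is a narrower claim and a few sentences of text. No scans, subjects or radiation are added. A re-run with noise raised to joint-scan levels is not requested, because it needs randoms or count data that the documents do not show reaching the company. A claim about simultaneous scanning itself would need acquired simultaneous or phantom data.

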6.2. Dual- vs. Single-Tracer Performance Assessments

The PET images for each tracer pair will be co-registered and combined to synthesize corresponding dual-tracer images. Dual-tracer processing algorithms, based on modeling differences in radioactive decay rates and kinetic distributions for each tracer, will be developed that take simultaneous dual-tracer PET images as input and out separate, recovered images of each individual tracer. The performance of the dual-tracer scanning approach and processing algorithms will be evaluated by comparing output images for each tracer to the corresponding original single-tracer images for that tracer. A number of analyses will be performed on these data.

In the following paragraphs, “recovered” is used to denote measures (image pixel values, SUVs) for individual-tracer images recovered from the dual-tracer images, and “true” is used to denote the corresponding value from the original constituent single-tracer image. This analysis evaluates how accurately the simultaneous dual-tracer imaging technique can recover individual images of each tracer, as compared to the images from conventional single-tracer scans.

